- Untreated or inadequately treated mental illness (indicators would include symptoms such as psychosis, hallucinations, mania, and any psychiatric hospitalization in the last year), or treatment with anti-psychotic medications that are known to affect glucose regulation.
- Electrically powered implants (e.g. cochlear implants, neurostimulators) that might be susceptible to RF interference
- History of adverse reaction to glucagon (including allergy) besides nausea and vomiting
- History of severe milk allergy
- Established history of allergy or severe reaction to adhesive or tape that must be used in the study
- Use of oral (e.g. thiazolidinediones, biguanides, sulfonylureas, glitinides, DPP-4 inhibitors, SGLT-2 inhibitors) anti-diabetic medications
- Use of parenteral diabetes medications other than insulin (e.g. amylin mimetics or GLP-1 receptor agonists)
- Chronic use of drugs with strong anticholinergic actions, including over-the-counter products (intermittent use is allowed as long as the drug is not taken on the day of experiments)
- Any factors that, in the opinion of the principal investigator would interfere with the safe completion of the study
- Hemoglobin < 12 g/dl
- Any subjects who develops an exclusionary condition during the study will be withdrawn
- Infusion Set Sub-Study:
 - Unable to provide informed consent (e.g. impaired cognition or judgment)
 - Unable to safely comply with study procedures and reporting requirements (e.g. impairment of vision or dexterity that prevents safe operation of their insulin pump, impaired memory, unable to speak and read English)
 - Pregnancy (positive urine HCG), breast feeding, plan to become pregnant in the immediate future, or sexually active without use of contraception
 - Hemoglobin < 11 g/dl
 - Unable to establish IV access, or subject reports difficult IV access in the past

History of allergy or severe reaction to adhesive or tape that must be used in the study

III. c. Source of Subjects

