Other studies have provided information on infusion site reactions when delivering smaller quantities of Xeris glucagon as a single injections. In one study, 0.075 mg of Xeris glucagon was delivered as a single injection, with no comparator arm. In that study, a burning sensation at the injection site was the most common reaction, occurring in 58% of subjects and numbness at the injection site occurred in 17% of subjects. There were no instances of well defined erythema in any subjects (n=12) administered this dose. In another study, small doses of Xeris glucagon or Novo glucagon (0.3, 1.2, and 2.0 mcg/kg) were administered as a single injection using an Omnipod patch pump. In this study, infusion site erythema and edema were the most common

AEs, and these occurred more commonly with Xeris than Novo glucagon (47% vs. 11% and 32% vs. 6%, respectively). Most cases were mild and transient for both formulations.

The bionic pancreas administers a maximum 0.08 mg per injection, and does this rarely. More typical doses of glucagon are in the range of 0.005-0.04 mg per dose. We do not have data on the tolerability of doses in this size range, nor on intermittent dosing at a single site, as will occur in this study. The incidence of other AEs with Xeris glucagon in human studies were low and were not different between Xeris and Lilly glucagon.

Both the iPhone-based and iLet bionic pancreas systems could administer isolated insulin–glucagon doses once every 5 minutes. A single automated bolus of insulin will not exceed 3 units per 5-minute dose [30 µl of U-100 insulin] in both systems, and a single meal-priming dose, in response to a meal announcement made by the user, will not exceed 12 units [120 µl of U-100 insulin]. A single bolus of glucagon will not exceed 80 µg [80 µl of 1 mg/ml Lilly glucagon, 16 µl of 5 mg/ml Xeris glucagon]. The t:slim insulin pumps used in the iPhone-based bionic pancreas are capable of administering as little as 0.5 µl (0.05 units of U-100 insulin or 0.5 µg of 1 mg/ml Lilly glucagon) in single programmable bolus doses. The iLet bionic pancreas is capable of administering as little as 0.11 µl (0.011 units of U-100 insulin or 0.55 µg of 5 mg/ml Xeris glucagon).

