This study is considered moderate risk. An external Data and Safety Monitoring Board will oversee the conduct of the study and review its results on a regular basis. Additionally, the DSMB will be informed in the event of any severe or unexpected adverse events. The DSMB will be informed if there are any changes to the study protocol that could significantly impact the safety or scientific validity of the study. A final DSMB meeting will convene after the completion of the study. Safety and efficacy data will also be reported to the FDA in compliance with applicable regulations.

As noted above, the participation of individual subjects will be discontinued if they experience:

- Seizure or unconsciousness associated with hypoglycemia
- Persistent nausea and vomiting thought to be related to glucagon dosing
- Persistent moderate or severe pain, edema or erythema at an infusion site
- Diabetic Ketoacidosis

If more than 1 subject must be withdrawn from the study for these reasons, the study will stop and a vote of the DSMB will be required to restart it. All serious and unexpected events will be reported to the DSMB within 72 hours.

Note that subjects may discontinue participation at any time and subjects may be removed from the trial for other reasons, for instance failure to comply with study procedures or intercurrent illness that is unrelated to the bionic

pancreas but that precludes safe participation. Discontinuation of participation for these reasons will not contribute to a decision to discontinue the trial.

IX. c. Adverse Event Reporting Guidelines

The PI and co-investigators will review any adverse events after each experiment. Any serious or unexpected but possibly related adverse events will be communicated to the PI as soon as possible and within 48 hours of the time they are detected. Adverse events will be reported promptly to the Partner's IRB. Collaborator [name] is the sponsor of the Investigational Device Exception (IDE) for the bionic pancreas to be used in this trial. Reports of adverse events will be made to the FDA in compliance with the terms of IDE.

X. Subject Compensation

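### In Aims 1 and 2, withdrawal for systemic allergy to study glucagon is required by III.b but does not count toward the automatic stop in IX.b

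*Combined protocol and SAP*

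**What the plan says.** Two sections bear on this.

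**III.b, Exclusion Criteria.** One criterion reads "History of adverse reaction to glucagon (including allergy) besides nausea and vomiting". Near the end of the main-study list comes the general rule: "Any subjects who develops an exclusionary condition during the study will be withdrawn".

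**IX.b, Safety Monitoring.** Four reasons for discontinuing an individual subject are listed: a seizure or loss of consciousness from hypoglycemia; "Persistent nausea and vomiting thought to be related to glucagon dosing"; a lasting infusion-site reaction of at least moderate severity; and ketoacidosis. The stopping rule follows: "If more than 1 subject must be withdrawn from the study for these reasons, the study will stop", with a DSMB vote needed to restart. The next paragraph allows removal on other grounds, "for instance failure to comply with study procedures or intercurrent illness that is unrelated to the bionic" pancreas, and closes: "Discontinuation of participation for these reasons will not contribute to a decision to discontinue the trial".

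IX.b also provides for reporting. An external DSMB is told of severe or unexpected adverse events, and a deadline is set: "All serious and unexpected events will be reported to the DSMB within 72 hours".

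**The concern.** The stopping rule is a hard brake: two product-related withdrawals, then a halt until the DSMB votes. It already counts glucagon-related nausea and vomiting, and local reactions at the infusion site. The paragraph on uncounted removals gives only examples unrelated to the product, so the apparent intent is to leave those out and count the rest. Systemic allergy to study glucagon is product-related, and III.b makes withdrawal mandatory, yet it adds nothing to the count.

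The result is uneven. Two subjects with persistent vomiting from glucagon stop the study automatically; two with generalized hypersensitivity to the same drug do not. The brake matters most where experience is thin. Aim 2 gives glucagon in a DMSO-based vehicle, and V.b says there are no tolerability data for doses of this size or for intermittent dosing at one site.

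**Working it through.** The stopping threshold is a rule, not a derived figure, so there is no plan calculation to reproduce. The check has two parts.

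**1. Apply the two sections to the same cases.**

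| Withdrawals, Aims 1 and 2 | Count under IX.b as written | Automatic stop? | Count if glucagon allergy were listed |
|---|---|---|---|
| Two persistent site reactions | 2 | Yes | 2 |
| Two persistent glucagon-related vomiting | 2 | Yes | 2 |
| One systemic glucagon allergy and one ketoacidosis | 1 | No | 2 (stop) |
| Two systemic glucagon allergies | 0 | No | 2 (stop) |

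The last two rows follow whichever way the paragraph on other removals is read. If its examples define the uncounted class, allergy falls outside that class but is still not among the four counted reasons. If the class is open-ended, allergy is uncounted outright.

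Two limits on scope:
- An allergy that shows as a persistent moderate or severe site reaction already counts under the third listed reason. The gap is systemic or other non-local allergy.
- The Infusion Set Sub-Study gives no glucagon, so only Aims 1 and 2 are affected.

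The origin is probably an oversight, though that is an inference. The IX.b list points back to earlier text and matches the response rules in V.d.6 to V.d.9. Section V.d has no response rule for allergy, so there was nothing to carry forward from it.

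**2. How often would two allergic withdrawals occur?**

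Inputs:
- n = 10 subjects dosed, from the up to 10 completers in IV.a.
- p = chance per subject, over all glucagon visits, of withdrawal for glucagon allergy. The documents give no rate. V.b says only: "The incidence of other AEs with Xeris glucagon in human studies were low and were not different between Xeris and Lilly glucagon". A range of 0.5% to 2% is assumed.
- Subjects are taken as independent with a common p.

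Formula: P(2 or more) = 1 − (1 − p)^n − n·p·(1 − p)^(n−1).

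- p = 0.005: 1 − 0.9511 − 0.0478 = 0.0011, or 0.1%
- p = 0.01: 1 − 0.9044 − 0.0914 = 0.0043, or 0.4% (from unrounded terms)
- p = 0.02: 1 − 0.8171 − 0.1667 = 0.0162, or 1.6%

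If all 20 enrollable subjects were dosed, the same formula gives 0.4%, 1.7% and 6.0%. That is a ceiling, since IV.a sets 20 partly to allow for subjects excluded after screening.

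**The case against.** The best reply is that nothing here is contradictory. A withdrawal list and a stopping list need not match: the III.b sentence covers every exclusion, including pregnancy and low hemoglobin, and nobody would want all of those to halt the study. The glucagon criterion is also phrased as history, which is screening language.

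Much of the risk is handled elsewhere too. An RN or MD is with subjects throughout (V.d.12). At most two subjects take part at once (V.d.4). Aim 1 data are analyzed before any Xeris visit (Aim 2, section II). Adverse events are reviewed after each experiment, and serious or unexpected, possibly related ones reach the principal investigator within 48 hours (IX.c). Prior glucagon reactors are screened out.

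Most of this stands, and it is why the point is minor. It does not remove the point. The lists need not match in general, but IX.b sets its own dividing line by example, and a drug allergy falls on the product-related side. The history wording does not help, because a subject who has reacted has that history from then on and may still have glucagon visits to come. The safeguards make sure people know; none supplies the automatic halt.

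Some stronger readings are tempting but unsupported:
- *The DSMB is barred from stopping for allergy.* A reader might infer this from the sentence that other removals do not contribute to a decision to discontinue. But its examples are unrelated to the product, and IX.b gives the DSMB oversight of the whole study. Nothing limits its discretion over a drug allergy.
- *Every on-study reaction to glucagon forces an uncounted withdrawal.* Taken literally the criterion might reach mild site reactions or headache, but V.d.9 already handles site reactions by moving the set first. No change to III.b is needed.
- *A combined chance of a stop can be quoted for allergy plus site reactions.* The documents give neither rate, and such a figure would set the other three counted reasons to zero. It would not be the stop probability under IX.b.

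**Conclusion.** The point holds as a minor one, confined to Aims 1 and 2 and to systemic or other non-local allergy. As written, such withdrawals add nothing to the stopping count at any rate. Two of them, or one with one other counted event, would leave the study running unless the DSMB chose to act.

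The event is unlikely: 0.1% to 1.6% for two or more allergic withdrawals among 10 dosed subjects, resting wholly on the assumed 0.5% to 2% per subject and on independence. The route through one allergy plus another counted event is not quantified, because the documents give no rates for it. The finding that the stop would not apply rests on the text alone and needs none of these assumptions.

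**What to change.** Add a fifth bullet to the counted list in IX.b: *Allergic (hypersensitivity) reaction attributed to study glucagon*. Name glucagon rather than study drug. The broader term would also take in insulin lispro and the Infusion Set Sub-Study, where this gap does not arise and which the figures above do not cover. Leave III.b unchanged.

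The cost is one line of text, with no added subjects, visits or data. The downside is a slightly higher chance of a halt and a DSMB vote: at most 1.6% from two allergic withdrawals with 10 subjects dosed and a rate of 2% or less, plus an unquantified amount from an allergy occurring alongside another counted event.

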We hypothesize that the iLet BP will be non-inferior to the iPhone-based BP in dose administration and blood glucose control while subsequently improving user satisfaction with the device. We also hypothesize that Xeris glucagon in the iLet BP will be non-inferior to Lilly glucagon in the iLet BP in both infusion site reactions and occlusions.

In the Infusion Set Sub-Study, we hypothesize that the iLet infusion set will be non-inferior to the Contact Detach infusion set in plasma insulin levels, blood glucose control, and user experience.

The specific aims of this study are:

Aim 1. To conduct an outpatient study testing the safety and efficacy of the iLet BP versus our iPhone-based BP in up to 10 adult (≥ 18 years of age) subjects with type 1 diabetes in the fasted state, after a meal, and during and after exercise.

The study for this Aim will consist of two 8-hour study arms in random order: one with the iPhone-based BP and one with the iLet BP. Subjects will arrive fasting and remain fasted until the lunch meal. They will exercise on a stationary bike bpm for approximately 30 minutes with a heart rate from 120–140, starting at least 2 hours after lunch. The primary outcome will be the average percent dose amounts of both insulin and glucagon calculated by the control algorithm that are successfully delivered by the pump. Important secondary outcomes will include other metrics of device function (plasma insulin and glucagon levels will be measured every 30 minutes throughout the experiment) and measures of glycemic regulation, including mean CGM glucose and hypoglycemia exposure (% time <60 mg/dl).

Aim 2. To conduct an outpatient study testing the safety and efficacy of the iLet BP with Lilly glucagon versus Xeris glucagon in up to 10 adult (≥ 18 years of age) subjects with type 1 diabetes

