To achieve this second Aim we will conduct an additional, third 8-hour study arm with the iLet BP using Xeris glucagon, which will be compared to the 8-hour study arm with the iLet BP using Lilly glucagon. The data from Aim 1 will be analyzed prior to initiation of the Aim 2 visit. If the performance of the iLet BP in the studies of Aim 1 visits is as expected, we will proceed to the visits of Aim 2. Subjects will arrive fasting and remain fasted until the lunch meal. They will exercise on a stationary bike bpm for approximately 30 minutes with a heart rate from 120–140, starting at least 2 hours after lunch. The primary outcome will be the average percent of glucagon calculated by the control algorithm that is successfully delivered by the pump. Important secondary outcomes will include infusion site reactions at the glucagon site, subject reported nausea, glucagon exposure (plasma insulin and glucagon levels will be measured every 30 minutes throughout the experiment), and measures of glycemic regulation, including mean CGM glucose and hypoglycemia exposure (% time <60 mg/dl).

Aim 3. To document the satisfaction of subjects with the iLet BP device with the goal of optimizing user interaction with the iLet.

Questionnaires will be administered at the beginning of the study and at the end of each arm to gather data on attitudes towards bionic pancreas usability, BG control, quality of life and treatment satisfaction. The primary analysis will include data from the first 2 arms (iPhone BP and iLet BP with Lilly glucagon) so that the analysis will be focused entirely on the performance of the BP platform and not the glucagon. A structured phone interview will be conducted with each participant after they have completed all of the visits to compare their experiences. This information will be used to make the best choices about how the final version of the bionic pancreas should be configured.

Aim 4. To conduct an in-clinic study comparing the performance of an investigational infusion set designed for use with the iLet Bionic Pancreas versus an FDA approved infusion set in up to 10 adult subjects with type 1 diabetes in both the fasted and post-prandial states.

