- Once all of the results have been returned, a study MD will review the case report form to determine subject eligibility. If subjects are not eligible to continue in the study the results of abnormal tests will be reported to the subjects and to a health care provider of their choosing.
- Subjects who have been screened and are eligible can participate without having to be re-screened for a period of one year. The study staff should verbally confirm that there have been no health events that would make them ineligible if the interval between screening and participation is longer than 3 months.
- Subjects who participated in Aim 1 and/or Aim 2 will be eligible to participate in Aim 4, but will have to be rescreened if it has been more than 1 year.

V. d. 2. Visit Order: Once the subject has been enrolled and eligibility of subjects has been established, the order of the visits using Lilly glucagon with the iPhone based system and the iLet system will be randomized in blocks of two subjects. The experiments of Aim 2 (iLet BP with Xeris glucagon) will be performed after the first two visits.

The order of the visits for the Infusion Set Sub-Study of Aim 4 will be randomized in blocks of two subjects, separately from the visits for Aim 1 and Aim 2.

V. d. 3. Training Visit: A training visit will take place before the first bionic pancreas visit. Subjects will be

trained in the insertion and calibration of the Dexcom G4 sensor, insertion of infusion sets, use of the two bionic pancreas systems and study policies and procedures. Study staff will verify that the subjects have understood the material and are competent to participate safely in the study.

A training visit is not required for the Infusion Set Sub-Study.

V. d. 4. Bionic Pancreas Visits

- Up to 2 subjects may participate at the same time.
- Each subject will participate in the bionic pancreas visit three times: once with the iPhone-based BP, once with the iLet BP using Lilly glucagon and once with the iLet BP using Xeris glucagon.
- The night before the visit, subjects will place a Dexcom G4 CGM sensor that is provided by the study team, and calibrate the sensor when prompted using the provided Nova Biomedical Statstrip Xpress meter. Subjects will be instructed to call if they encounter any difficulty with their CGM.

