The main criteria for the success of the study will be that we observe a significant improvement in the primary outcome measure (and the related secondary reliability measures) in the iLet vs. the iPhone-based BPs, and no significant difference in the glycemic control measures. It is possible that improved reliability may actually improve glycemic control measures, but the sample size may not be sufficient to detect any such difference. A secondary criterion for success of the study will be that we observe no statistical difference in safety-related outcomes (occlusions, infusion site reactions or pain, nausea) between Xeris and Lilly glucagon.

The main criteria for the success of the infusion set sub-study will be that we observe no significant difference in the performance of the iLet infusion set when compared with the Contact Detach. Achieving a non-inferior result would allow us to move forward in future testing of the iLet infusion set with the iLet bionic pancreas in outpatient trials.

VII. Risks and Discomforts

Subjects may experience mild discomfort associated with the insertion of the infusion sets and sensor into the SC tissues. The risk of discomfort due to insertion of infusion sets and sensors is expected to be greater than in their lives outside the trial because more infusion sets will be inserted and a CGM sensor will be inserted, which may not be used in usual care.

There is a potential risk of hypoglycemia, since exogenous insulin will be administered. Due to frequent monitoring of glucose and direct supervision by an RN or MD at all times, the risk of a hypoglycemic episodes leading to significant harm to volunteers is expected to be substantially lower than their risk during their usual therapy.

There is a risk of hyperglycemia. This risk is expected to be less than the risk during the subjects' lives outside of the trial based on data from earlier trials.

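### Xeris glucagon is always given at the third visit, so Aim 2 cannot separate formulation from visit order, yet the plan reads the Xeris-Lilly difference as a formulation result

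*Combined protocol and SAP*

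**What the plan says.** Each subject has three bionic pancreas visits (V.d.4: "Each subject will participate in the bionic pancreas visit three times"): iPhone-based system with Lilly glucagon, iLet with Lilly glucagon, and iLet with Xeris glucagon.

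- **Order (V.d.2).** For the Lilly visits, the order of the iPhone-based system and "the iLet system will be randomized in blocks of two subjects". For the Xeris visit: "The experiments of Aim 2 (iLet BP with Xeris glucagon) will be performed after the first two visits".
- **Reason for the order (II, Aim 2).** "The data from Aim 1 will be analyzed prior to initiation of the Aim 2 visit". Aim 2 goes ahead only if the iLet has performed as expected in Aim 1.
- **Contrast and primary outcome (II, Aim 2).** The Xeris visit is the one "which will be compared to the 8-hour study arm with the iLet BP using Lilly glucagon". On the endpoint: "The primary outcome will be the average percent of glucagon calculated by the control algorithm that is successfully delivered by the pump".
- **Hypothesis (II).** "Xeris glucagon in the iLet BP will be non-inferior to Lilly glucagon in the iLet BP", for infusion site reactions and occlusions.
- **Success criterion (VI.d).** A secondary criterion asks for "no statistical difference in safety-related outcomes (occlusions, infusion site reactions or pain, nausea) between Xeris and Lilly glucagon".
- **Analysis (end of VI.b).** Each comparison uses a paired t-test or Wilcoxon signed-rank test, without a period term. A secondary analysis looks for period effects and treatment-by-period interaction. The only caveat is that power may be too low for a small interaction.

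Nowhere is the fixed position of the Xeris visit named as a limitation.

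**The concern.** A paired test in a crossover can be read as a treatment effect because randomised order balances the treatments over visits. That holds for iLet versus iPhone. It does not hold for Xeris versus Lilly, because no subject receives Xeris before visit 3 and none receives Lilly at visit 3. Anything that differs at a third visit falls on the Xeris side: subjects' and staff's growing experience with insertion and handling, habituation to site pain or nausea, and calendar time. The protocol describes no masking of the Xeris visit, and several of the safety outcomes are rated by the subject or judged by observation.

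The error could run either way, but the success criterion rewards a null result. Section V.b reports more erythema (47% vs 11%) and edema (32% vs 6%) with Xeris than with another glucagon after single small doses, and says there are no tolerability data for intermittent dosing at one site. A favourable drift by visit 3 could hide a difference of that kind.

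The secondary period analysis may reassure a reader that order has been dealt with. For Aim 2 it has not: the obstacle is that the two effects cannot be told apart, not that power is low.

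**Working it through.** **Inputs.** Visit order from V.d.2; three visits per subject from V.d.4; up to 10 completers from IV.a; paired tests from VI.b; two-sided 5% level from VI.c, where it is given for Aim 1. An even split of five subjects per sequence is assumed, which blocks of two should produce.

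**The plan's own figure.** There is none for Aim 2. The Aim 1 sizes in VI.c follow from n = 2(1.960 + 0.842)² × 2.5² / δ² = 98.1/δ². For δ = 2.0, 3.2 and 3.6 points this gives 24.5, 9.6 and 7.6, rounded up to 25, 10 and 8, as stated. They concern iLet versus iPhone and do not bear on this point.

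**Step 1: sequences.** Let A = iPhone-Lilly, B = iLet-Lilly, C = iLet-Xeris. The only possible sequences are ABC and BAC.

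**Step 2: what the paired difference estimates.** Let π1, π2, π3 be the visit effects and τ the formulation effect (Xeris minus Lilly in the iLet).

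- Sequence ABC: E(C − B) = τ + π3 − π2
- Sequence BAC: E(C − B) = τ + π3 − π1
- Average over equal groups: τ + π3 − (π1 + π2)/2

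**Step 3: can a period term separate them?** With 10 subjects, the model has 10 subject + 2 visit + 2 treatment = 14 columns and 30 rows. Its rank is 13. The visit-3 and Xeris columns are identical (correlation 1.0), so τ is not estimable once visit is in the model. The iLet versus iPhone contrast remains estimable because A and B are balanced over visits 1 and 2.

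**Step 4: possible size.** The documents give neither an order effect nor an SD of the paired difference for any Aim 2 outcome, so the shifts below are assumptions. For a continuous outcome, paired t-test, n = 10, two-sided 5%, the noncentrality is (shift in SD) × √10. With τ = 0:

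| Net shift (SD of paired difference) | Probability of p<0.05 |
|---|---|
| 0 | 5% |
| 0.3 | 13.6% |
| 0.5 | 29.3% |
| 0.8 | 61.6% |

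Conversely, a true difference of 1.0 SD is detected with 80% power when there is no order effect, and with 29% if an opposite shift halves it.

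**Step 5: what an assumption can buy.** Let d = π2 − π1, which Aim 1 estimates.

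- Plateau after visit 2 (effects 0, d, d): bias = d − 0.5d = 0.5d
- Linear drift (effects 0, d, 2d): bias = 2d − 0.5d = 1.5d

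With residual variance σ² and n = 10, the unadjusted contrast has variance 2σ²/10 = 0.20σ². The estimate of d also has variance 0.20σ² and, with balanced sequences, is uncorrelated with the contrast. Subtracting 1.5d gives 0.20 + 1.5² × 0.20 = 0.65σ², which is 3.25-fold higher. Subtracting 0.5d gives 0.20 + 0.5² × 0.20 = 0.25σ², which is 1.25-fold higher.

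**The case against.** The case for leaving the plan alone has real content.

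- **The order is a deliberate gate.** Aim 1 is analysed before Xeris is used. This stands, and the point does not ask for a different order.
- **The criterion is secondary, in a small early device study.** This also stands. It limits the importance of the point but does not make the Xeris-Lilly claim interpretable.
- **Order effects may be small.** Subjects are trained on both systems before the first visit (V.d.3). The algorithm starts each visit from body weight alone (V.d.4), so no learned dosing carries over. Nausea, pain and Draize scores are taken against each visit's own baseline (VI.b.5). Section VII reports no significant nausea difference against usual care in earlier studies. Habituation cannot act directly on the device-recorded percentage of glucagon delivered. These points make a large shift less likely; they do not exclude learning, habituation of response or calendar effects.
- **The plan already examines period.** It does, and for Aim 1 this is useful. For Aim 2 it cannot work.

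A reader might infer three stronger things that the documents do not support. First, that the device will be altered between Aim 1 and Aim 2: no section plans this, and IV.a expects completers under a consistent protocol. Second, that the percentages in the table are error rates of the VI.d criterion: occlusions are probably sparse counts and Draize scores are ordinal, and VI.b would use the Wilcoxon test for non-normal residuals. Third, that reporting separately by the position of the iLet-Lilly visit would resolve the matter: five subjects per group widen the 95% interval half-width from about 0.72 SD (2.262/√10) to about 1.24 SD (2.776/√5), and visit 3 would still be only Xeris.

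**Conclusion.** The point holds as a limit on what Aim 2 can conclude. Formulation and visit 3 are completely aliased; this follows from the visit order alone and needs no assumption about the size of any order effect. The paired difference equals the formulation effect only if the visit-3 effect matches the average of the visit-1 and visit-2 effects, which these data cannot test.

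How much this distorts the result is unknown. The 14%, 29% and 62% rest on assumed shifts, a continuous and roughly normal outcome, and 10 complete pairs.

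A reader might go further and conclude that the trial's main result is compromised. It is not: the main criterion compares iLet with iPhone, whose order is randomised. The missing non-inferiority margin, and the reading of a non-significant test as absence of a difference, are separate weaknesses that would exist under any order and add no weight here.

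**What to change.** Keep the staged order and change the wording and reporting.

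1. In section II (hypothesis and Aim 2) and in VI.d, state that Aim 2 is a non-randomised sequential comparison in which Xeris always follows Lilly.
2. In the analysis text of VI.b, state that the period and interaction analysis applies to Aim 1 only.
3. Report the Xeris-Lilly difference with a 95% confidence interval for all subjects together.
4. Replace the non-inferiority wording in II and the Xeris criterion in VI.d with a descriptive conclusion, for example: no large safety signal seen; formulation and visit order not separable.
5. Optionally, add a sensitivity analysis that subtracts 0.5d (plateau) and 1.5d (linear drift), with d estimated in Aim 1. Show both and label them as assumption-based and imprecise.

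The cost is a few sentences and at most one extra analysis, with no added visits or subjects. The real price is a weaker Aim 2 claim. A design that kept the gate and still separated the effects would need a further randomised iLet-Lilly/iLet-Xeris crossover after Aim 1, hence one more iLet-Lilly visit per subject; a descriptive conclusion does not require it.
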